5.1 Collection of Key Efficacy Measurement and Derivation of Key Efficacy Variable

In this long-term extension study no primary or secondary efficacy variable has been defined. However, the key efficacy measure is the change from baseline to posttreatment in the normalized daily average frequency of daytime urinary incontinence episodes (daytime is defined as the time between waking up to start the day and going to bed to sleep for the

night). The daily average frequency of daytime urinary incontinence episodes is obtained using the total number of daytime urinary incontinence episodes recorded in a 2-day bladder diary divided by 2, and study baseline frequency is defined as the daily average frequency of episodes of daytime urinary incontinence preceding the study treatment in study 191622-120.

Each daytime period recorded in the bladder diary is normalized to represent a 12-hour period to account for differing durations of the daytime period (see Section 2.3 for further details). Furthermore, if there is just 1-day valid bladder diary data, this will be used as the daily average frequency of daytime urinary incontinence episodes (see Section 2.3 for further details).

The key time point for this change from baseline endpoint will be week 6 after each treatment/injection.

5.2 Key Efficacy Analyses

Since there is no primary efficacy measure, this section describes the analysis for the key efficacy variable.

For each cycle, for each post-treatment visit, mean values and mean change from study baseline values for the daily average frequency of normalized daytime urinary incontinence episodes will be presented together with the associated t-distribution based 95% CIs for the mean change from study baseline. This summary will be presented for each BOTOX treatment group of that cycle. This summary will also be repeated for the non-normalized daily average frequency of daytime urinary incontinence episodes. The key timepoint for analysis for each cycle is week 6 posttreatment.

For patients that increased their BOTOX dose from 50 U to 100 U or from 100 U to 200 U a paired difference will be derived between the lower dose cycle and the subsequent higher dose cycle's week 6 daily average frequencies normalized daytime urinary incontinence episodes values. These values will be summarized using mean paired difference, associated standard error and paired t-test.

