#### General Statistical Methods and Types of Analyses:

One analysis population will be used in the statistical analysis of this study: the BOTOX-treated population. Data from the patients' participation in this extension study (191622-121) will be integrated with the corresponding patients' data from the preceding study (191622-120). Thus, the BOTOX-treated population will include all patients enrolled into the extension study who have received at least 1 BOTOX treatment over the course of the total evaluation period.

All efficacy and safety analyses will be based on the treatment actually received in each treatment cycle. Patients will be grouped to the nearest dose group (50, 100, or 200 U BOTOX) based on the dose actually received.

There will be no hypothesis testing in this long-term extension study. All data will be summarized with descriptive statistics and/or frequency tables.

For efficacy analysis, week 6 after each treatment will be the timepoint of main interest and the efficacy variable of key focus is change from baseline in the daily average frequency of daytime urinary incontinence episodes. Data will be presented by BOTOX treatment cycle according to the dose received at that treatment cycle (grouped to the nearest dose group, ie, 50, 100, or 200 U BOTOX), as well as by an overall BOTOX group (ie, regardless of dose). For each BOTOX treatment cycle, descriptive statistics will be provided for the daily average frequency of daytime urinary incontinence episodes at baseline and each posttreatment visit. The change from baseline (arithmetic mean and least-squares [LS] mean) and the 95% confidence intervals (CI) of the arithmetic and LS mean change will be provided.

Other efficacy analyses will include the proportions of patients achieving  $\geq 50\%$ ,  $\geq 75\%$ ,  $\geq 90\%$ , and 100% reduction from baseline in daytime urinary incontinence.

[figure not shown]
Duration of effect will be evaluated as time from study drug administration to request for retreatment, and dose-response analyses will include a nonparametric area under the curve (AUC) analysis of daily average frequency of daytime urinary incontinence episodes.

For other efficacy and health outcomes variables, descriptive statistics will be provided.

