# 5.5 Method for Assignment to Treatment Groups/Randomization

There will be no randomization in this long-term extension study.

All patients who receive treatment in this study will receive BOTOX. The blinded dose received (50, 100, or 200 U BOTOX, not exceeding 6 U/kg) will be dependent on the assessment of the clinical response (efficacy and safety) to the previous blinded study treatment (which will have been 50, 100, or 200 U BOTOX, not exceeding 6 U/kg). The patient/parent/caregiver will be questioned on their treatment response to establish if, in their opinion, the current treatment response is adequate or if there was little or no treatment benefit and whether they would be willing/want to have a higher dose. They will also be questioned on whether the patient is experiencing side effects. Using this information, the investigator will use his/her own clinical assessment of the patient and apply the following criteria for the retreatment dose request:

- if the benefit/risk balance is evaluated by the investigator to be appropriate at the current dose, then the same dose would be requested
- if the investigator assessed that, although the preceding dose was well tolerated, the
  response received was insufficient and warrants a higher dose, then a dose increase would
  be requested

• if the investigator assessed that there were side effects that would warrant a lower dose, the patient would be exited from the study

Compared to the previous treatment, the investigator therefore has the following options:

- elect to keep the same dose as received at the previous treatment (not to exceed 6 U/kg)
- elect to increase the dose compared to the previous treatment (not to exceed 6 U/kg):
- if the patient received 50 U BOTOX at the previous treatment, they would receive 100 U BOTOX
  - if the patient received 100 U BOTOX at the previous treatment, they would receive 200 U BOTOX
  - if the patient received 200 U BOTOX at the previous treatment, they would remain at 200 U BOTOX (after 2 requests to increase the dose from 200 U the patient will be exited; see below)

At the qualification for retreatment visit the investigator or designee will contact the IVRS/IWRS and indicate the treatment option for the patient. IVRS/IWRS options will be either to remain at the same dose or to increase the dose since patients will be exited from the study if the investigator assessed that a lower dose was warranted (see below).

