### 7.3.1.1 Efficacy Analyses for Daytime Urinary Incontinence Episodes

For each BOTOX treatment cycle, descriptive statistics will be provided for the daily average frequency of daytime urinary incontinence episodes at baseline and posttreatment visits. The change from baseline (arithmetic mean and least-squares [LS] mean) and the 95% confidence intervals (CI) of the arithmetic and LS mean change will be provided.

A responder analysis for daytime urinary incontinence will be performed using different thresholds of reduction from baseline. A patient will be considered a treatment responder if they have at least a 50% reduction from baseline in daytime urinary incontinence, however other thresholds will also be evaluated. The proportion of patients with  $\geq$  50%,  $\geq$  75%,  $\geq$  90%, and 100% reduction from baseline in daytime urinary incontinence will be presented by BOTOX treatment cycle for each posttreatment visit.

In addition the change from baseline and responder analyses will be performed using the normalized daily average frequency of daytime urinary incontinence episodes; these analyses will also be conducted without the normalization of the variable to a 12 hour daytime period.

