When all patients in study 191622-120 exit the study, there will be a data base lock (DBL) for study 191622-120 and a subsequent interim analysis for study 191622-121. A separate analysis plan is available with details of the interim analysis for study 191622-121. After this interim analysis the patients, investigator and Allergan staff will all be unblinded.

10. Analysis for US FDA

Not applicable.

11. Data Collected but not Analyzed

A patient's surgical history and female patients' birth control treatment during the study are collected in this study. No output will be generated for these data.

12. Deviations from Protocol

The number of patients that have reduction from baseline in daytime urinary incontinence episodes that meet certain threshold will not be analyzed using the non-normalized daytime rates of incontinence episodes. However, the non-normalized daily average frequency of daytime urinary incontinence episodes will be summarized.

13. References

14. Amendments

Following is a summary of content-oriented changes that were made to each section of the SAP, and a brief rationale for these changes. Minor editorial and document formatting revisions have not been summarized.

Amendment 1

Sections	Revision	Rationale
Section 2.1: Analysis Populations	Additional text included to clarify how participants are assigned to actual BOTOX treatment group based on actual dose administered.	To clarify how participants are assigned to actual BOTOX treatment group based on actual dose administered.
Section 2.3: Data Conventions	Modified imputation rules for completely missing or partial dates for adverse events and prior/concomitant medications	To reflect current company standard
Section 5: Efficacy Analyses	Subgroup analyses of key efficacy variable was removed	Only a subset of participants exit study 191622-120 and enroll in study 191622-121. These subgroup analyses are performed in study 191622-120
Section 6.2: Adverse Events	Section was re-written to reflect current company standard. For example updated definition of treatment-emergent adverse event	To reflect current company standard

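### The protocol commits to a least-squares mean change with a 95% CI for the key efficacy variable; SAP 5.2 plans only the arithmetic mean change and SAP 12 does not declare the omission

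*SAP*

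**What the plan says.** Protocol 7.3.1.1 sets out the summary of the key efficacy variable for each treatment cycle: "The change from baseline (arithmetic mean and least-squares [LS] mean) and the 95% confidence intervals (CI) of the arithmetic and LS mean change". The Protocol Summary, under general statistical methods, repeats the commitment: "95% confidence intervals (CI) of the arithmetic and LS mean change will be provided". Neither place names the model or the covariates behind the LS mean. ANCOVA and ANOVA appear only in the protocol's glossary.

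SAP 5.2 plans for the same variable that "mean values and mean change from study baseline values for the daily average frequency of normalized daytime urinary incontinence episodes will be presented", accompanied by "t-distribution based 95% CIs for the mean change from study baseline". It repeats this for the non-normalized frequency and adds a within-patient paired difference for patients whose dose was increased. No LS mean and no adjusted model appears in the visible SAP.

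SAP 12 (Deviations from Protocol) declares one departure: the responder thresholds "will not be analyzed using the non-normalized daytime rates of incontinence episodes". The SAP amendment log has one entry for Section 5: "Subgroup analyses of key efficacy variable was removed". Neither mentions LS means.

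On allocation, Protocol 5.5 states: "There will be no randomization in this long-term extension study". The investigator chooses to keep or raise the dose after judging the response to the previous treatment. SAP 2.1 then places each patient-cycle in a dose column by the dose actually received.

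**The concern.** Half of the promised summary of the key variable is missing from the SAP, and the section meant to record departures is silent on it. A reader of the final report could not tell whether the LS mean was dropped on purpose, and for what reason, or was overlooked.

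The omission matters most for how the dose columns read side by side. From cycle 2 a child's column depends on a clinical decision, so mean baseline frequency may differ between columns. A reduction in episodes cannot be larger than the child's baseline count, so a column holding children with more baseline episodes can show a larger raw reduction at the same drug effect. The SAP also removes the protocol's subgroup summaries of this variable by baseline frequency and age. No visible summary of mean change across dose columns then takes either factor into account.

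**Working it through.** **Step 1: text comparison.** There is no sample size, power or alpha figure to reproduce on this point. The core of it is a comparison of the two documents.

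| Item | Protocol Summary and 7.3.1.1 | SAP 5.2 |
|---|---|---|
| Arithmetic mean change, 95% CI | yes | yes, t-based |
| LS mean change, 95% CI | yes | absent |
| Model and covariates | not named | none |
| Removal declared | not applicable | not in SAP 12, not in the amendment log |

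SAP 5.2 and SAP 12 read as complete on this point, so redaction does not explain the gap.

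**Step 2: is a baseline-adjusted LS mean the natural reading?** In a model with dose group alone, the LS mean equals the arithmetic mean (only the CI could differ, through a pooled variance). Promising both therefore suggests a model with covariates. That is an inference, because the protocol does not say so.

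**Step 3: size of the baseline effect.** Inputs, both assumed because the documents give no SDs, slopes or column baselines: a baseline gap of 1 episode/day between two columns, and a slope of change on baseline of -0.5 to -0.8.

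Difference in raw mean change with no dose effect = slope × gap
- -0.5 × 1 = -0.5 episodes/day
- -0.8 × 1 = -0.8 episodes/day

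**Step 4: effect of adjustment on CI width.** Assumed inputs: three equal groups of n = 26 (the 78 patients expected in SAP 1.1.1, divided by 3); r = size of the correlation between baseline and change; d = distance of a column's baseline mean from the overall mean, in within-group SDs. The within-group sum of squares in those units is 78 - 3 = 75.

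CI width ratio (LS / arithmetic) = [t(0.975; 74) / t(0.975; 25)] × √(1 - r²) × √(1 + n·d²/75)

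The t ratio is 1.993 / 2.060 = 0.967. At d = 1 the last factor is √(1 + 26/75) = 1.160.

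| r | √(1 - r²) | d = 0 | d = 1 |
|---|---|---|---|
| 0.3 | 0.954 | 0.923 | 1.071 |
| 0.5 | 0.866 | 0.838 | 0.972 |
| 0.7 | 0.714 | 0.691 | 0.802 |

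With balanced baselines the LS mean CI is narrower throughout. With a column 1 SD from the overall mean, it is about 7% wider at r = 0.3, about 3% narrower at r = 0.5 and about 20% narrower at r = 0.7. The gain is therefore smallest, and can reverse, in the imbalanced situation that motivates the adjustment.

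**Step 5: is an age covariate workable?** SAP Table 1 puts doses of 150 U or more in the 200 U column, and the cap is 6 U/kg. Since 150 / 6 = 25 kg, a child under 25 kg dosed within the cap cannot be in that column. Age is thus tied to dose column through weight, and some age-by-dose cells may be nearly empty.

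**The case against.** The strongest reply is that little depends on this. The study tests no hypotheses, defines no primary efficacy variable, and keeps the arithmetic mean and CI that the protocol also promised. The dependence on baseline is already partly handled. The responder proportions in SAP 5.3.1 are relative to each child's own baseline, the paired difference in SAP 5.2 is within patient, and a column's baseline mean can be recovered from its mean value and mean change. Cycle 1 columns derive from a randomized study, though only for patients who rolled over. This limits the consequence. It does not explain the omission, because the protocol promised LS means in the same plan that excludes hypothesis testing.

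Three stronger readings are tempting, and the documents do not support them.

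- A reader might infer that the protocol promised a baseline-adjusted estimate. It names no model or covariate; adjustment is only the likeliest meaning.
- A reader might infer that the SAP's estimates are less precise than the promised ones. The documents give no SD or correlation, and Step 4 shows that the direction depends on the imbalance.
- A reader might infer that restoring the LS mean would make the dose columns comparable. From cycle 2 the dose follows the response to the previous treatment, and study-baseline frequency does not capture that response. Selection would remain after adjustment.

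**Conclusion.** The mismatch is established from the text: an LS mean change with a 95% CI is promised twice in the protocol, is absent from SAP 5.2, and is not declared in SAP 12 or the amendment log. No assumption is needed for that.

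The consequence is moderate. Raw changes in side-by-side columns may carry a baseline difference, illustrated at 0.5 to 0.8 episodes/day for an assumed 1 episode/day gap and an assumed slope of -0.5 to -0.8. The actual gap and slope are unknown. An LS mean adjusted for study baseline would remove that measured part and nothing else. No general claim of narrower CIs is justified. The change should be made because it concerns the key variable and is cheap, although no decision rule in the study depends on it.

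**What to change.** In SAP 5.2, for each cycle and post-treatment visit, add an ANCOVA of change in normalized daily frequency on dose group, with study-baseline normalized frequency as the fixed covariate. Report the LS mean change and its 95% CI per dose group beside the arithmetic mean, with no p-values. Add age stratum (<12, ≥12 years) as a second covariate only under a minimum cell size written into the SAP beforehand, so that the model is not chosen after seeing the data.

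State in the SAP and under the tables that the adjustment addresses measured baseline imbalance only and does not make dose groups selected by prior response comparable.

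The cost is SAP wording, one short model and an extra column in tables already planned. The downside is that the LS mean CI may be slightly wider where a column's baseline lies far from the overall mean.

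If the sponsor prefers to leave the LS mean out, list its removal in SAP 12 with the reason. That costs one or two sentences.

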5.3 Other Efficacy Analyses

In this section all the other efficacy variables and analyses are discussed.

5.3.1 Analysis of the Number of Patients that have Reduction from Baseline in Daytime Urinary Incontinence Episodes that meet Certain Thresholds

The number of patients that have a reduction from baseline in daily average frequency of normalized daytime urinary incontinence episodes of at least 50%, 75%, 90%, and 100% will be summarized within each treatment cycle, by providing the percentages and the associated 95% confidence intervals, by the treatment group for each posttreatment visit. The 95% confidence interval will be derived using the exact Clopper-Pearson confidence limits for the binomial proportions.

5.3.2 Urine Volume at First Morning Catheterization (mL)

For urine volume at first morning catheterization (mL), for each BOTOX treatment cycle, the mean study baseline, mean raw values and mean change from study baseline and associated 95% CI for the mean change from study baseline will be derived for each visit by treatment group.

5.3.3 Presence or Absence of Night Time Urinary Incontinence

For the analysis of night time urinary incontinence, for each BOTOX treatment cycle, the numbers (percentage) of patients who experienced night time urinary incontinence on 0, 1, or 2 nights will be presented at study baseline and at each visit. For each visit there will be two sets of percentages. The first set of percentage will be for patients that have just one valid diary day and the second set will be for patients that have two diary days i.e., the numerator for the percentage calculation will be the patients that have the given number of diary days.

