2.3.1 Data Conventions Limited to Diary data

- Study baseline diary information refers to the baseline information collected at the start of study 191622-120 (see Section 2.2).
- For study baseline and post-treatment visits, analyses will be based on the diary data collected over two consecutive days. For each day, the bladder diary will be used to collect date, time, and type of voiding episode (urinary incontinence, catheterization, or voluntary void) for each daytime episode (time between waking up to start the day and going to bed to sleep for the night). Furthermore, volume of urine on catheterization at morning wakening, the time the patient went to bed to sleep at night and the time the patient woke up in the morning and presence/absence of night time urinary incontinence will be collected for each diary day.

- The visit windows defined in Section 2.2 will be used to derive a patient's diary parameters for each visit.
- A valid diary day is defined as a day where there are one or more urinary episodes of any type (incontinence, catheterization, or voluntary void) during the daytime collection period. In the case of patients who provide just one valid diary day within a visit window, the 2-day frequency of daytime urinary incontinence will be prorated with the value from the valid diary day.
- If there are no valid diary days within the window, the 2-day diary data will be set as missing for the visit.
- For baseline and post-treatment visits, the 2-day diary will be determined based on the following algorithm:
 - 1) Apply visit windows defined in Section 2.2, which are based on days from the date of study drug injection.
 - 2) Determine the time of the first daytime urinary episode that is within the visit window (in the example below, 8:30 am on May 4). Count forward two consecutive daytime diary collection days. Note: the second daytime period should end within the window, i.e., prior to or on the last day specified in the window definition; otherwise, the nighttime or daytime data will not be used for the corresponding window. For baseline diary data, any urinary episode collected up to the time of injection will be counted towards the baseline diary data.

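### SAP 5.3.3 names the patients with a given number of diary days as the numerator of the night-time incontinence percentages; that group is the denominator, and none is stated.

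*SAP*

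**What the plan says.** SAP 5.3.3 states that, for each cycle, "the numbers (percentage) of patients who experienced night time urinary incontinence on 0, 1, or 2 nights will be presented at study baseline" and again at each visit. It continues: "For each visit there will be two sets of percentages". The split is by amount of diary data: "The first set of percentage will be for patients that have just one valid diary day and the second set will be for patients that"; the sentence then specifies two diary days for that second set. The section closes with the calculation rule, that "the numerator for the percentage calculation will be the patients that have the given number of diary days". It gives no denominator.

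The validity of a diary day is defined in SAP 2.3.1: "A valid diary day is defined as a day where there are one or more urinary episodes of any type", which the text then limits to "incontinence, catheterization, or voluntary void) during the daytime collection period". Night status is a separate diary item: "presence/absence of night time urinary incontinence will be collected for each diary day". The same section adds: "If there are no valid diary days within the window, the 2-day diary data will be set as missing for the visit".

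Protocol 7.3.1.3 plans the number and proportion of patients by number of wet nights and does not define the base. SAP section 12 (deviations from the protocol) and the log of two SAP amendments in section 14 do not mention this analysis.

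**The concern.** A percentage of patients in a night category needs two things: the patients in that category on top, and the patients who could have been in it underneath. The SAP puts the second group on top and leaves the bottom empty. Followed to the letter, the percentage does not depend on whether anyone was wet at night.

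Presence or absence of night-time incontinence is one of the efficacy variables listed in Protocol 7.2.1, and SAP 5.3.3 is its only analysis in the SAP. The table is repeated by cycle, visit and dose group, so an unclear base would carry through many cells. Sponsor staff and sites are to be unblinded after the interim analysis (Protocol 7.7, SAP 9). The base is therefore better fixed in the text than chosen at programming.

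A smaller, related point is that the sets are formed by diary days while the variable concerns nights. Whether a day counts depends on daytime entries, and nothing in the available text ties it to the night entry being filled in.

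**Working it through.** The documents give no percentage, power or sample-size figure on this point, so there is nothing of the plan's own to reproduce. The check compares readings of the rule on an assumed visit.

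**Assumed inputs (not from the documents).** 40 patients have diary data at the visit. Of these, 4 have one valid diary day and 36 have two, with 2 to 10 one-day patients as the range. The two-day patients split roughly 40/30/30 over 0, 1 and 2 wet nights, which for 36 patients is 14, 11 and 11.

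**Reading A, literal.** Numerator = all patients with two diary days, in every row.
- Over all 40 patients: 36/40 = 90% in the 0-, 1- and 2-night rows alike.
- Over the two-day patients themselves: 36/36 = 100% in every row.
- Range: 38/40 = 95% with 2 one-day patients, and 30/40 = 75% with 10.
- In the one-day set the same rule gives 4/40 = 10% in every row. That includes the 2-night row, which a patient contributing one night cannot enter.

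**Reading B, category patients with two diary days over all patients with diary data.** This is possible because no denominator is stated.
- 14/40 = 35.0%, 11/40 = 27.5%, 11/40 = 27.5%; the sum is 90%.
- Over the range of one-day patients the sum runs from 95% to 75%.

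**Reading C, category patients over patients with two diary days.**
- 14/36 = 38.9%, 11/36 = 30.6%, 11/36 = 30.6%; the sum is 36/36 = 100% apart from rounding.
- With 2 one-day patients (38 two-day, split 15/11/12): 39.5%, 28.9%, 31.6%.
- With 10 one-day patients (30 two-day, split 12/9/9): 40.0%, 30.0%, 30.0%.

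Only Reading C matches the description of two sets, each for patients with a given amount of diary data. The counts of 14, 11 and 11 are the same under all three readings.

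**Validity, text against text.** SAP 2.3.1 makes a day valid if there is at least one daytime episode. Night presence or absence is a separate entry on that day. Two cases are therefore not settled by the definition: a day that is valid with a blank night entry, and a night entry on a day with no daytime episode. For the second, the SAP sets the whole two-day diary to missing if no day in the window is valid, so a recorded night would be dropped. For the first, no rule was found.

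**The case against.** The strongest reply is that this is one wrong word with an obvious meaning. The opening sentence of SAP 5.3.3 says which patients are counted, and the next describes each set as being for patients with one or two days, which is the language of a base. A competent programmer would be unlikely to produce a table with identical rows. The counts are reported whatever happens to the percentages, so it would be wrong to say that the distribution of wet nights could not be seen. The table is descriptive and sits under other efficacy analyses. The key variable is daytime episodes, and Protocol 7.3 plans no hypothesis testing. All of this stands, and it limits how much weight the point carries. It does not make the stated rule right. Because no denominator is given, Reading B also remains open to a programmer who only partly repairs the sentence.

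A reader might go further and infer that blank nights will be read as dry, so that the table leans toward dryness. The documents do not support that. No passage says a blank counts as dry, and absence is itself a recorded answer, distinct from a blank. Protocol 6.1.1 also refers to Section 6.3.5 for diary details, and that section is not in the public text, so a recording rule may exist there. How often nights are left blank is unknown. The daytime criterion itself may exclude few days, since patients regularly use catheterization.

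**Conclusion.** The calculation rule in SAP 5.3.3 is wrong as written. It names the base of each set as the numerator, which gives one value for all rows, and it states no denominator. No other section of either document corrects it. The intent is clear enough that the wording is probably a slip, and the counts stand.

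On the assumed visit, the gap is between 90% in every row and 38.9%, 30.6% and 30.6%. These figures depend on the assumed 40 patients and their split, and serve only to show what the rule does. No error rate, power or key result is affected.

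The validity point holds only as a mismatch: diary days are judged by daytime episodes, while the variable is recorded per night. It is a reason to define the denominator by nights. It is not evidence that the percentages are biased, and neither a direction nor a size can be given.

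**What to change.** In the last sentence of SAP 5.3.3, replace *numerator* with *denominator*. Add that the numerator is the number of patients in each night category: 0 or 1 for the one-day set, and 0, 1 or 2 for the two-day set. Define the denominator as patients with one, or two, nights on which presence or absence of incontinence was recorded, so that a night without an entry is missing for this table.

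The cost is one or two sentences in the SAP. A few nights may become missing, and a patient with one recorded night out of two would move to the one-night set. No data collection changes.
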